2.16 Interim analysis

No interim analysis will be conducted.

3 Sample size calculation

A total sample size of 60 patients, randomized 2:1 to ofatumumab and placebo, will provide more than **90% power** for a statistical test of superiority of ofatumumab compared with placebo at a one-sided alpha level 0.025. The power was calculated based on a negative binomial model under the assumption of 1.0 Gd-enhancing T1 lesions per scan for placebo and a 92% relative reduction with ofatumumab (i.e. 0.08 Gd-enhancing T1 lesions per scan for ofatumumab), and a dispersion parameter $\kappa = 4.5$ (as observed in the combined Phase 3 placebo-controlled studies of fingolimod, namely FREEDOMS and FREEDOMS II studies for the same parameter, data on file). The sample size allows for a dropout rate of 10%.

Sample size calculation was done in EAST 6, version 6.3, Cytel Inc.

3.1 Evaluation of consistency in the treatment effect on the primary variable across regions

As a secondary objective the effect of ofatumumab on Gd-enhancing T1 lesion compared with placebo will be estimated for individual regions (Japan and other countries). It is planned to include 30 patients from Japan out of 60 in total.

The randomization will be stratified by region (Japan or other countries), and by Gd-lesion status on the screening scan (0 Gd-enhancing T1 lesions or ≥ 1 Gd-enhancing T1 lesions). Under the protocol assumptions for placebo, it is expected that approximately 2/3 of the patients will be free of Gd-enhancing T1 lesions at baseline.

A simulation was performed to evaluate the consistency in efficacy on the primary variable across regions. Consistency is defined as a rate ratio < 1 in both Japan and other countries. For the simulation the following assumptions apply:

- The assumptions for the primary variable are the same for Japan and other countries and identical to those for the primary endpoint (i.e. 1 Gd-enhancing T1 lesion per scan, a rate-ratio of 0.08 between ofatumumab and placebo, dispersion 4.5)

- In addition, it was assumed that the study would include 30 patients from Japan and 30 from other countries, and that patients would be randomized 2:1 to ofatumumab or placebo group in each region.

The probability to observe a consistent treatment effect between Japan and other countries was estimated to be higher than 99% under these settings.

Furthermore, we estimated the probability to observe a difference in treatment effect (percentage lesion reduction between ofatumumab and placebo) between Japan and other countries under the same assumptions. The probability to observe a difference of 20% or more (one-sided) in treatment effect between Japan and other countries was estimated to be < 3% ([Table 3-1](#)).

Table 3-1 Probability to observe a difference in Gd-lesion reduction across regions of more than delta

Delta*	Probability of a difference in percentage lesion reduction > Delta
5%	13.7%
10%	6.1%
20%	2.3%
30%	1.3%

*Delta=Percentage lesion reduction for other countries - percentage lesion reduction for Japan

3.2 Numerical comparison of annualized relapse rate (ARR)

As a secondary objective the ARR will be compared between patients treated with ofatumumab or placebo. We evaluated the probability to observe a treatment effect in favor of ofatumumab, as defined by an ARR-ratio (ofatumumab/placebo) less than 1 in the overall population. The following assumptions were made for this evaluation:

- 60 subjects in total are randomized 2:1 to ofatumumab or placebo.
- The true ARRs are 0.4 in the placebo arm, and 0.16 in the ofatumumab arm.
- The dispersion parameter, k , is 0.1.
- The follow-up period is 6 months.

Under these settings, the probability to observe a lower ARR in patients treated with ofatumumab compared with placebo is > 80%.

4 Changes to protocol specified analyses

Below changes to protocol specified analyses are included in this document:

1. Cut-off 2 analysis will be conducted when the last patient completes all assessments up to the Week 48 visit, which includes all data from the Safety FU period obtained up to the date of Cut-off 2 as defined above.
2. Final analysis will be conducted when all patients completed the EOS visit or Safety FU period.

3. Used 100 days for Safety cut-off instead of 30 days based on the half life of the compound.
4. Removed Time to first confirmed relapse from the sensitivity analyses section.
5. Defined a simpler negative binomial model with only treatment and region (Japan or other countries) as factors as a fallback option on the ARR analysis and time to first confirmed relapse analysis, in case the model specified in the protocol do not converge or has other statistical limitations.

5 Appendix

5.1 Imputation rules

5.1.1 Study drug

Missing or partial dates are not allowed in completing the study drug administration CRF pages. The end date of study drug will be the last end date or last injection date for patients randomized to ofatumumab or placebo, respectively.

5.1.2 AE date imputation

For the start and end dates of the adverse event records, when incomplete or missing, dates will be imputed according to Novartis standards (details will be given in PDS document).

5.1.3 Concomitant medication date imputation

For the start and end dates of the concomitant medication records, when incomplete or missing, dates will be imputed according to Novartis standards (details will be given in PDS document).

5.1.3.1 Prior therapies date imputation

Same as above.

5.1.3.2 Post therapies date imputation

Same as above.

5.1.4 Relapse date imputation

Missing or partial dates are not allowed for completing the start date of relapses on the MS relapses CRF pages. Sites are required to provide best estimate if patients don't have the exact date. In the rare cases when partial date (unknown day with month and year available) exist in the final database, the following rule will apply:

- A partial start date will be imputed by the first day of the month or the first dose date if it occurs in the same month as the first dose date.
- A partial end date will be imputed by the last day of the month or truncated to have a duration of maximally 90 days.

5.1.5 Other imputations

For the calculation of duration or time since relevant history events as specified in section 2.3.3 (MS disease baseline characteristics), partial dates will be imputed for the MS diagnosis start date, the first MS symptom date, the most recent relapse onset date via below imputation rules.

- If the year is missing or impossible (e.g. 12-Jan-1911), then the date will be imputed as missing.
- If the year is not missing and possible, but the month is impossible or missing (e.g. 17-XXX-2010), then the year will be kept and date will be imputed as July 1st (e.g., 1-July-2010).
- If the year and the month are not missing and possible, but the day is impossible or missing (e.g., 31-FEB-2009), then the year and month will be kept, and date will be imputed as 15th (e.g., 15-FEB-2009).
- The imputed dates should be prior to the screening visit date. That is, if imputed dates are on or after the screening visit date, the dates will be imputed to be one day before the screening visit date.

5.1.5.1 Data manipulation for relapses within 30 days of onset of previous relapses or relapses with duration beyond 90 days

According to protocol definition of MS relapses, the start date of a new relapse has to be at least 30 days after the start date of a previous relapse (i.e., start date of a new relapse – start date of a previous relapse ≥ 30). If a relapse is recorded with a start date less than 30 days after the start date of a previous relapse, below data manipulation will be done to combine them into a single relapse by creating a new relapse record with the following information.

- Start date: take the earliest start date.
- End date: take the latest end date. If one of the end dates is missing, set it to missing.
- Date of EDSS intended to confirm the relapse:
 - Take the date of EDSS by which the relapse can be confirmed.
 - If more than one EDSS assessments meet the above criteria, take the date of EDSS by which the worst severity value is derived.
 - If no EDSS assessment meets the above criteria, take the earliest date of EDSS as captured on the relapse CRF page.
- Severity: take the value representing the worst case (severe>moderate>mild>missing)
- “Did the relapse affect daily activities?”, “Hospitalization?”, “Steroid used?”, “Recovery status”: for each of these characteristics, take the value representing the worst case (yes>no for first 3 questions; no>partial>complete recovery for last question).

According to CRF completion guidelines, maximum duration of a relapse is 90 days. If a relapse is recorded with a duration longer than 90 days, the end date will be truncated to have a duration of exactly 90 days. This applies also to the artificial record created by above procedure.

5.2 AEs coding/grading

AEs are coded using the Medical dictionary for regulatory activities (MedDRA) terminology. The latest MedDRA version will be used and will be described in the footnote of relevant outputs.

AEs will be assessed according to the Common Terminology Criteria for Adverse Events (CTCAE) version 5.0.

The CTCAE represents a comprehensive grading system for reporting the acute and late effects of cancer treatments. CTCAE grading is by definition a 5-point scale generally corresponding to mild, moderate, severe, life threatening, and death. This grading system inherently places a value on the importance of an event, although there is not necessarily proportionality among grades (a grade 2 is not necessarily twice as bad as a grade 1). The CTCAE grade of 5 (death) is not used; rather, “fatal” is collected as AE outcome and death information is also collected on a separate CRF page.

5.3 Laboratory parameters derivations

For each patient, the estimated creatinine clearance values (without collecting urine) will be calculated using the Cockcroft-Gault formula (as specified in [Table 5-1](#)). In these calculations, the body weight is the last measurement collected on or before the day when the patient takes the laboratory test and age should also be calculated based on the time when the patient takes the laboratory test.

If the creatinine value is collected in the unit μ mol/L (SI unit), it will be converted to mg/dL in order to use the formulas. The conversion is via the equation below:

- $\text{mg/dL} = 88.4 \mu\text{mol/L}$ (e.g., creatinine = 2.0 mg/dL = 176.8 $\mu\text{mol/L}$).

Table 5-1 Creatinine clearance calculation

Variable	Formula
Creatinine clearance [mL/min] Using Cockcroft-Gault formula	$= (140 - A) * W / (72 * C) * G$ Where A is age [years] W is body weight [kg] C is the serum concentration of creatinine [mg/dL] G is a constant: G=1 for males and G=0.85 for females.

The estimated creatinine clearance will be included as one of the laboratory parameters.

5.3.1 Laboratory test groups and subgroups

On presenting lab results, grouping parameters by family will ease the review. Table below shows a possible set of lab parameters and their corresponding classification.

Table 5-2 Laboratory tests

Order	Laboratory Group Subgroups	Tests [SI unit]	
1	Hematology		
	Red Blood Cells	Hematocrit [%] Hemoglobin [mmol/L] Platelets [10E9/L] Red cell count [10E12/L]	
	White Blood Cell Differential	Absolute Basophils [10E9/L] Absolute Eosinophils [10E9/L] Absolute Lymphocytes [10E9/L] Absolute Monocytes [10E9/L] Basophils [%] Eosinophils [%] Lymphocytes [%] Monocytes [%] Neutrophils [%] White Cell Count [10E9/L]	
	B-cells	CD19+ B-cell counts [cells/ μ l]	
	T-cells	CD3+ CD20+ T-cell counts [cells/ μ l]	
			
	Immunoglobulin	Total IgG [g/L] Total IgM [g/L]	
	2	Chemistry	
		Renal Function	Creatinine [μ mol/L] Blood urea nitrogen [mmol/L]
		Liver Function Test	ALT [U/L] Albumin [g/L] Alkaline Phosphatase [U/L] AST [U/L] Bilirubin (direct/conjugated) [μ mol/L] GGT [U/L] Total Bilirubin [μ mol/L] Total protein [g/L]

Order	Laboratory Group Subgroups	Tests [SI unit]
	Other Enzymes	Amylase [U/L]
	Lipids	Cholesterol HDL [mmol/L] Cholesterol LDL [mmol/L] Triglycerides [mmol/L] Total Cholesterol [mmol/L]
	Other	Random glucose [mmol/L] C-Reactive protein CRP [mg/L]
	Electrolytes / Metabolism Tests	Bicarbonate [mmol/L] Calcium [mmol/L] Chloride [mmol/L] Magnesium [mmol/L] Phosphate [mmol/L] Potassium [mmol/L] Sodium [mmol/L]
3	Urinalysis	Blood Glucose Specific gravity Albumin Protein

5.3.2 Newly occurring liver enzymes abnormalities

Below lists the criteria for “events” of newly occurring liver enzymes abnormalities:

- ALT > 3, 5, 10, 20x ULN
- ALT or AST > 3, 5, 8, 10, 20x ULN
- AST > 3, 5, 8, 10, 20x ULN
- ALT or AST > 3x ULN & TBIL > 1.5x ULN
- ALT or AST > 3x ULN & TBIL > 2x ULN

- ALP > 1.5, 2, 5x ULN
- TBIL > 1, 1.5, 2x ULN
- ALP > 3, 5x ULN & TBIL > 2x ULN

- ALT or AST > 3x ULN & TBIL > 2x ULN & ALP ≤ 2x ULN

When a criterion contains multiple laboratory parameters (e.g., ALT > 3xULN & TBL > 2xULN), unless otherwise requested by the project clinical team/Brand Safety Leader (BSL), the criterion should be only considered to be met when the elevation in both parameters occurs on the same sample day (as evidenced by the same date that the lab samples were taken).

The “events” are defined in the Novartis safety guideline on hepatotoxicity, section: Safety parameters for special liver event analyses.

5.3.3 Newly occurring renal events

Below lists the criteria for newly occurring renal events:

- SCr increase ≥ 25% and <50% from baseline
- SCr increase ≥50% from baseline
- New onset dipstick proteinuria (confirmed) (≥ 1+)
- New onset dipstick glycosuria (≥ 1+)
- New onset dipstick hematuria (≥ 1+)

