7.4 Renal safety monitoring

The following two categories of abnormal renal laboratory values should be considered during the course of the study:

- Serum event:
 - confirmed (after \geq 24 hours) increase in serum creatinine (sCR) of $\geq 25\%$ compared to baseline during normal hydration status
- Urine event
 - new onset ($\geq 1+$) proteinuria; confirmed by doubling in the urinary albumin/creatinine ratio (ACR) or urinary protein-creatinine ratio (PCR) (if applicable)
 - new onset ($\geq 1+$), hematuria or glycosuria

Every renal laboratory trigger or renal event as defined in [Table 14-1 in Appendix 2](#) should be followed up by the Investigator or designated personnel at the trial site as summarized in [Appendix 2](#). The renal AE/SAE and any contributing factors (concomitant medications, other co-morbid conditions/procedures) should be recorded in the appropriate CRFs.

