ALP (isolated)	Repeat LFT within 48 hours If elevation persists, establish causality Record AE/SAE and any contributing factors (concomitant medications, other co-morbid conditions/procedures) in the appropriate CRFs	Investigator discretion Monitor LFT within 1 to 4 weeks or at next visit
TBL (isolated)	Repeat LFT within 48 hours If elevation persists, discontinue the study drug immediately Hospitalize if clinically appropriate Establish causality Record AE/SAE and any contributing factors (concomitant medications, other co-morbid conditions/procedures) in the appropriate CRFs	ALT, AST, TBL, Alb, PT/INR, AP and GGT until resolution ^c (frequency at Investigator discretion) Test for hemolysis (e.g., reticulocytes, haptoglobin, unconjugated [indirect] bilirubin)

Criteria	Actions required	Follow-up monitoring
> 1.5 to \leq 2 \times ULN (patient is asymptomatic)	Repeat LFT within the next week If elevation is confirmed, initiate close observation of the patient	Investigator discretion Monitor LFT within 1 to 4 weeks or at next visit
Jaundice	Discontinue the study treatment immediately Hospitalize the patient Establish causality Record AE/SAE and any contributing factors (concomitant medications, other co-morbid conditions/procedures) in the appropriate CRFs	ALT, AST, TBL, Alb, PT/INR, AP and GGT until resolution ^c (frequency at Investigator discretion)
Any AE potentially indicative of a liver toxicity*	Consider study treatment interruption or discontinuation Hospitalization if clinically appropriate Establish causality Record AE/SAE and any contributing factors (concomitant medications, other co-morbid conditions/procedures) in the appropriate CRFs	Investigator discretion

^aElevated ALT/AST > 3 \times ULN and TBL > 2 \times ULN but without notable increase in AP to > 2 \times ULN

^b(General) malaise, fatigue, abdominal pain, nausea, or vomiting, or rash with eosinophilia

^cResolution is defined as an outcome of one of the following: (1) return to baseline values, (2) stable values at three subsequent monitoring visits at least 2 weeks apart, (3) remain at elevated level after a maximum of 6 months, (4) liver transplantation, and (5) death.

PT=prothrombin time

14 Appendix 2: Specific Renal Alert Criteria and Actions

Table 14-1 Specific Renal Alert Criteria and Actions

Serum Event	
Serum creatinine increase 25-49% compared to baseline	Confirm 25% increase after 24-48 hours Follow-up within 2-5 days

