Acute Kidney Injury: Serum creatinine increase ≥ 50% compared to baseline	Follow-up within 24-48h if possible Consider study treatment interruption Consider patient hospitalization/specialized treatment
Urine Event	
New dipstick proteinuria ≥ 1+ Albumin- or Protein-creatinine ratio increase ≥ 2-fold Albumin-creatinine ratio (ACR) ≥ 30 mg/g or ≥ 3 mg/mmol; Protein-creatinine ratio (PCR) ≥ 150 mg/g or > 15 mg/mmol	Confirm value after 24-48 hours Perform urine microscopy Consider study treatment interruption/or discontinuation
New dipstick glycosuria ≥ 1+ not due to diabetes	Blood glucose (fasting) Perform serum creatinine, ACR
New dipstick hematuria ≥ 1+ not due to trauma or menstruation	Urine sediment microscopy Perform serum creatinine, ACR
For all renal events:	
Record AE/SAE and any contributing factors (concomitant medications, other co-morbid conditions/procedures) in the appropriate CRFs.	
Monitor patient regularly (frequency at Investigator's discretion) until either: Event resolution: sCR within 10% of baseline or protein-creatinine ratio within 50% of baseline, or Event stabilization: sCR level with ±10% variability over last 6 months or protein-creatinine ratio stabilization at a new level with ±50% variability over last 6 months.	

15 Appendix 3: Safety monitoring Guidance

15.1 Guidance on monitoring of patients with symptoms of neurological deterioration suggestive of PML

Should a patient develop any unexpected neurological or psychiatric symptom/signs in the opinion of Investigator (e.g. cognitive deficit, behavioral changes, cortical visual disturbances or any other neurological cortical symptoms/signs any symptom/sign suggestive of an increase of intracranial pressure) or accelerated neurological deterioration, the Investigator should schedule a complete physical and neurological examination and an MRI as soon as possible before beginning any steroid treatment. Conventional MRI as defined in the protocol as well as additional scanning such as Fluid-Attenuated Inversion Recovery (FLAIR) and Diffusion-weighted imaging (DWI) sequences are recommended to aid in differential diagnosis. The MRI must be evaluated by the local radiologist/neurologist. The Investigator will contact the Medical Advisor at Novartis to discuss findings and diagnostic possibilities as soon as possible. A copy of the unplanned MRI should be sent to the MRI Evaluation Center designated by the Sponsor as soon as possible. AE/SAEs need to be filed as appropriate.

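### SAP 5.3.3 counts a renal event on any single creatinine value at least 25% above baseline, although protocol 7.4 defines the serum event as a confirmed rise

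*SAP*

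**What the plan says.** **Protocol 7.4 (Renal safety monitoring).** The serum event is an increase in serum creatinine of at least 25%, confirmed after at least 24 hours, "compared to baseline during normal hydration status". The urine events are new proteinuria, with a ratio-based confirmation, and new haematuria or glycosuria at 1+ or more. The section then points to Table 14-1 in Appendix 2 for the definition of renal triggers and events.

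**Protocol Table 14-1 (Appendix 2).** For a 25-49% rise the action is "Confirm 25% increase after 24-48 hours". For a rise of 50% or more it asks for follow-up within 24-48 hours if possible and does not use the word confirm. The haematuria row reads "New dipstick hematuria ≥ 1+ not due to trauma or menstruation"; the glycosuria row excludes diabetes.

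**SAP 2.8.3 and 5.3.3.** SAP 2.8.3 summarises the overall frequency of renal events and the percentage of patients with them, adds listings, and takes the definition from 5.3.3. The creatinine criteria there are "SCr increase ≥ 25% and <50% from baseline" and "SCr increase ≥50% from baseline". The proteinuria line begins "New onset dipstick proteinuria (confirmed) (≥ 1". Glycosuria and haematuria are listed at 1+ or more without further condition.

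**SAP Section 4.** Five changes from the protocol are listed. None concerns renal events.

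**The concern.** A reader of the study report will take the renal-event percentage to be the protocol's event. For creatinine it would not be: one value at or above 1.25 times baseline is enough. Because proteinuria alone carries a confirmation condition, a programmer would reasonably conclude that none applies to creatinine.

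Creatinine varies within a patient, each patient has several post-baseline samples, and all are compared with one baseline value. Some patients will cross 25% by chance, and confirmation is what removes most of these. In a trial of 60 patients, a few chance events could make up most of the renal table.

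**Working it through.** **1. Creatinine definitions side by side**

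| Rise | Protocol 7.4 | Table 14-1 | SAP 5.3.3 |
|---|---|---|---|
| 25% to below 50% | confirmed after at least 24 h | confirm after 24-48 h (an action) | single value |
| 50% or more | confirmed (covered by the 25% threshold) | follow-up, if possible within 24-48 h | single value |

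The mismatch with 7.4 covers both bands. The mismatch with Table 14-1 concerns the lower band only. I found no other SAP text that brings the confirmation back.

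**2. Size of the effect**

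The plan states no renal-event rate, so there is no figure to reproduce. The calculation below is an illustration.

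Inputs:
- Three Core post-baseline samples, at Weeks 4, 12 and 24 (SAP Table 2-3).
- 60 patients planned (SAP Section 3).
- Within-patient creatinine CV: **assumed**, because the documents give none. Range 5% to 10%.
- Log-normal values and no true change.

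Formulae:
- σ = √ln(1 + CV²), and the threshold is ln 1.25 = 0.2231.
- Given a baseline deviation b, one visit reaches the threshold with probability q(b) = 1 − Φ((0.2231 + b)/σ).
- Unconfirmed, any of three visits: average of 1 − (1 − q)³ over b.
- Confirmed by one independent repeat: average of 1 − (1 − q²)³ over b.

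Hand check at CV 8%: σ = 0.0799. The SD of a difference from baseline is 0.0799 × √2 = 0.1130, and 0.2231/0.1130 = 1.975, so a single visit reaches the threshold with probability 2.4%. Three visits give at most 3 × 2.4% = 7.2%; the shared baseline brings this down to 6.1%.

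| Assumed CV | Unconfirmed (SAP 5.3.3) | Confirmed, independent repeat (7.4) | Of 60 patients |
|---|---|---|---|
| 5% | 0.2% | 0.01% | 0.1 vs 0.01 |
| 8% | 6.1% | 1.1% | 3.7 vs 0.7 |
| 10% | 13.3% | 3.5% | 8.0 vs 2.1 |

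Simulation of 1,000,000 patients per setting and direct numerical integration agree with these values. Setting σ equal to the CV moves the last row to 13.4% and 3.6%.

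**3. Sensitivity to a correlated repeat**

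A repeat a day or two later may share a short-term cause with the first value. At CV 8%, if the two within-patient deviations correlate 0.5, the confirmed figure rises from 1.1% to 2.4% (60 × 0.024 = 1.4 patients). At 0.8 it is 3.7% (60 × 0.037 = 2.2 patients). The ratio of unconfirmed to confirmed falls from about 5 to 2.6 and then 1.7. These correlations are assumptions too.

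**4. Haematuria and glycosuria**

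The 7.4 bullet lists both without exclusions, and SAP 5.3.3 matches that bullet. Table 14-1 excludes trauma, menstruation and diabetes. The protocol therefore disagrees with itself, and the SAP follows one of its two texts.

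**The case against.** The case for leaving 5.3.3 alone has substance.

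- **Delegation.** Protocol 7.4 is a monitoring section. Protocol 9.5.2 leaves the analyses of additional safety assessments to the SAP, and 9.5.2.2 promises renal frequencies and listings without defining the event. An unconfirmed screen arguably falls within that latitude. This weakens the complaint about SAP Section 4, but it does not make the two events the same, and nothing tells the reader that they differ.
- **Sensitivity.** A sensitive single-value screen is a defensible safety choice, and the liver criteria in SAP 5.3.2 need no repeat either. Two rows keep that sensitivity.
- **Other views of the data.** Detailed renal listings, CTCAE grading of creatinine and adverse-event reporting of clinically significant values all remain. They limit the harm, but they do not correct the percentage.
- **Size.** At CV 5% the effect is negligible, and a correlated repeat narrows the gap. Both points stand.

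Three stronger readings are tempting but not supported. First, a reader might infer that the SAP breaks the protocol by counting menstrual haematuria or diabetic glycosuria; it agrees with 7.4 and differs only from Table 14-1. Second, a reader might infer that Table 14-1 requires a confirmatory sample for every creatinine event; its confirm instruction is in the lower band only. Third, a reader might infer a biased or diluted comparison between arms; the Core rule is identical in both, and SAP 2.8.3 plans no renal test or decision rule.

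**Conclusion.** The point holds for creatinine. As written, SAP 5.3.3 reports a broader event than protocol 7.4 defines, without saying so. With no true change, the share of patients counted in the Core part ranges from 0.2% to 13.3% unconfirmed over assumed CVs of 5% to 10%, against 0.01% to 3.5% confirmed with an independent repeat. At CV 8% it is 6.1% against 1.1%, or against 2.4% to 3.7% with a correlated repeat. All of these rest on a CV that the documents do not give.

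The consequence is an inflated and noisier descriptive safety percentage. The primary analysis is not touched. For haematuria and glycosuria the finding is narrower: two protocol passages conflict and must be reconciled. I take no view on which is right.

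**What to change.** 1. In SAP 5.3.3, report creatinine rises of at least 25% in two rows: confirmed by a repeat at least 24 hours later, as in protocol 7.4, and unconfirmed or not repeated. The existing bands can be kept within each row. This is a reporting rule and does not change what investigators do.
2. List in SAP Section 4 any departure that remains, including the hydration condition of 7.4 if hydration status is not available as data.
3. Reconcile protocol 7.4 and Table 14-1 on haematuria and glycosuria. Until the cause is shown to be captured as data, label those SAP rows as all-cause dipstick findings and apply no exclusion. Table 14-1 asks for contributing factors for renal events; a finding that the same table excludes may have no record of its cause.

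**Cost.** SAP wording, one extra row and a rule that pairs each trigger value with a later repeat. SAP 2.1.2 already brings unscheduled visits into the safety analyses. The downside is that patients without a repeat sample stay in the unconfirmed row. This may matter most for rises of 50% or more, where Table 14-1 asks only for follow-up if possible.
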